10 STATISTICAL ANALYSIS

10.1 General Considerations

In later sections, for analysis related to FAS, Safety Set, LCI Set [REDACTED] in Treatment Cohort Period 1, the population will not be limited to subjects in Treatment Cohort Period 1, regardless of the subtitle “Treatment Cohort Period 1”. The analysis will strictly follow their definitions in Section 8 of the SAP.

For subjects in the Observational Cohort, summaries will only be provided for the disposition, demographic and baseline characteristics, and SAEs. Summaries will be provided based on all enrolled subjects in the Observational Cohort.

For subjects in the Treatment Cohort Period 2, summaries will only be provided for the disposition, demographics, AEs, SAEs, LFTs, and ophthalmologic examinations analyses.

The Schedule of Assessments is provided in Appendix A.

Treatment Cohort Period 1

For Treatment Cohort Period 1, all analyses will be provided using all available data, regardless of whether subjects turned 12 years of age and subsequently switched to the higher dose with LUM 400 mg q12h/IVA 250 mg q12h.

The efficacy and safety analysis for different Study Periods will be based on different analysis set as summarized in Table 10-1.

Table 10-1 Analysis of Efficacy and Safety Based on Different Analysis Set in Different Study Periods

Period	Efficacy			Safety
Previous/Cumulative Study Period	FAS	109 FAS	LCI Set	Safety Set
Current Study Period	110 FAS	109 ROS	110 LCI Set	110 Safety Set

Continuous variables will be summarized using the following descriptive summary statistics: the number of subjects (n), mean, standard deviation (SD), standard error (SE), median, minimum value (min), and maximum value (max). Precisions of the summary for continuous variables are detailed in Table 13-4, Appendix B.

Categorical variables will be summarized using counts and percentages. Percentages will be presented to 1 decimal place.

Baseline: The baseline value of each Study Period for the Treatment Cohort Period 1 is defined as the most recent measurement (scheduled or unscheduled) before intake of the first dose of the corresponding Study Period, except if specified otherwise. These baselines are referred to as previous study baseline, current study baseline and cumulative study baseline.

- For LCI-related parameters, the values at each visit will be calculated based on the multiple replicates per the algorithm provided by the LCI central reader as detailed in Appendix C.

The baseline of LCI will be the most recent visit with non-missing value before the initial administration of study drug in the corresponding Study Period.

- For ECG, the baseline will be defined as the average of the 3 pretreatment measurements on the start of each Study Period.
- For sweat chloride, the values at each visit will be based on the averaged measurements from left and right arms.
 - The current study baseline will be the value at the most recent visit before the first dose of Study 110.
 - The previous study baseline and cumulative study baseline will be the baseline from the previous study, i.e., average of the values at screening and the pretreatment measurement on Day 1 from the previous studies. If only 1 sweat chloride measurement before the first dose is available, that measurement will be considered the baseline.

Absolute Change from baseline: will be calculated as Post baseline value - Baseline value.

Relative change from baseline: will be calculated and expressed in percentages as $100 \times (\text{Post baseline value} - \text{Baseline value}) / \text{Baseline value}$.

Unscheduled Visits: Unscheduled visit measurements will be included in listings, for derivation of visit windows and computation of baseline/last on-treatment visit, and for the analysis of maximum/minimum values and maximum/minimum changes from baseline values.

Visit Windows: Table 13-5 defines the visit window mapping rules to derive the actual visits for the scheduled post-baseline measurements.

Repeated observations within the same visit window

- For all efficacy parameters, if there are multiple measurements within a visit window, the record at the scheduled visit will be used. If there are no measurements at the scheduled visit, then 1) the record closest to the target day will be used; or 2) if there are multiple records with the same distance to the target day, the latest record will be used.
- For all safety parameters, if there are multiple measurements within a visit window, then 1) the record closest to the target day will be used; or 2) if there are multiple records with the same distance to the target day, the latest record will be used.

BMI, weight, and height will follow safety and efficacy windowing rules. For predose spirometry, efficacy windowing rules will be applied. For postdose serial spirometry, analyses will be based on nominal assessment.

Incomplete/Missing data will not be imputed, unless otherwise specified; i.e., all missing values will remain as missing in all statistical analyses and listings, unless otherwise specified.

Outliers: No formal statistical analyses will be performed to detect and/or remedy the presence of statistical outliers.

Repeated Observations: Measurements recorded at different time points are defined as repeated observations. If an assessment has planned repeated measurements, then statistical summaries will present all planned time points, as appropriate.

10.1.1 Efficacy Analysis Presentation Rules and Format

Treatment Cohort Period 1

For all continuous efficacy variables, change from previous study baseline with two treatment groups: L200/I-L/I and P-L/I, will be summarized descriptively and using a mixed model repeated measure (MMRM) model. The presentation format is provided in Table 10-2.

Descriptive summary of raw values and change from current study baseline for P-L/I will also be summarized in separate tables with one column.

Table 10-2 Continuous Efficacy Variable Summary Presentation Format

Summary statistics	109/011B and 110	
	L200/I-L/I	P-L/I
109/011B Baseline	xx	xx
109/011B Day 15	xx	xx
Change at 109/011B Day 15	xx	xx
...
109/011B Week 24	xx	xx
Change at 109/011B Week 24	xx	xx
110 Day 15	xx	xx
Change at 110 Day 15	xx	xx
...

10.1.2 Safety Analysis Presentation Rules and Format

10.1.2.1 Event Data

Treatment Cohort Period 1

Unless otherwise specified, incidence tables summarizing n and percentages for categorical safety data will be provided for:

- Previous Study Period (Studies 109/011B) based on the Safety Set with two treatment groups (L200/I, Placebo);
- Current Study Period (Study 110) based on the 110 Safety Set with two treatment groups (L200/I-L/I, P-L/I) and Overall;
- Cumulative Study Period based on Safety Set with L200/I-L/I, and Current Study Period based on 110 Safety Set with P-L/I, pooled together. The pooled treatment group is presented as L/I Overall.

Exposure-adjusted number of events will summarize number of events per 100 patient-year (100PY) for AE related safety data. Note: 1 patient with 48 weeks of exposure duration is defined as 1 patient-year (1PY). The exposure-adjusted number of events will be provided for the Study Periods with the analyses sets and treatment groups as defined above.

The categorical safety summary tables with incidence only will be presented in the table format as shown in Table 10-3. The categorical safety summary tables with both incidence and

exposure-adjusted number of events summaries will be presented in the table format as shown in Table 10-4.

Table 10-3 Presentation Format for Summary Tables of Categorical Safety Endpoints with Incidence Summary Only

109/011B		110			109/011B and 110	
L200/I	Placebo	L200/I-L/I	P-L/I	Overall	L/I Overall	

Table 10-4 Presentation Format for Summary Tables of Categorical Safety Endpoints with Both Incidence and Exposure-Adjusted Number of Events Summaries

109/011B				110				109/011B and 110			
L200/I		Placebo		L200/I-L/I		P-L/I		Overall		L/I Overall	
n (%)	Events/100PY	n (%)	Events/100PY	n (%)	Events/100PY	n (%)	Events/100PY	n (%)	Events/100PY	n (%)	Events/100PY

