Ongoing Studies 011 Part B and 109 are designed to obtain PK, safety, tolerability, PD, and efficacy (Study 109 only) information to support an expanded indication for lumacaftor and ivacaftor combination therapy in the pediatric population (subjects 6 through 11 years of age, inclusive, who are homozygous for the *F508del-CFTR* mutation). Study 109 is designed to compare active treatment (LUM 200 mg q12h/IVA 250 mg q12h) with a matched placebo treatment for 24 weeks.

The long-term safety of lumacaftor in combination with ivacaftor has not yet been evaluated in subjects aged 6 through 11 years. Therefore, the primary objective of this study is to evaluate the long-term safety and tolerability of lumacaftor in combination with ivacaftor in subjects aged 6 years and older with CF, homozygous for the *F508del-CFTR* mutation, and who rollover from Study 109 or Study 011 Part B.

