8.1 Efficacy Set

Full Analysis Set (FAS) includes all subjects who are randomized and dosed in Study 109, or subjects enrolled and dosed in Study 011B. The FAS treatment group assignment is shown in Table 8-1; the treatment group will be as randomized/enrolled in the previous studies.

Table 8-1 FAS Treatment Group Assignment in Study 110

Treatment Groups	Description
L200/I-L/I	Subjects randomized/enrolled to L200/I in the previous studies (Study 109 or Study 011B) ^a
P-L/I	Subjects randomized to placebo in Study 109 ^a

I: ivacaftor; L: lumacaftor; P: placebo.

^a Subjects who turn 12 years of age in the previous studies or Day 1 of this rollover study will begin receiving L400/I on Day 1. Subjects who turn 12 years of age after the Day 1 Visit of this rollover study will begin receiving L400/I at their next scheduled visit.

110 Full Analysis Set (110 FAS): The 110 FAS will include all subjects who rolled over from Study 109 and Study 011B, and who are enrolled and exposed to any amount of study drug in Study 110. The 110 FAS treatment group assignment is shown in Table 8-2; the treatment group will be as randomized/enrolled in the previous studies.

Table 8-2 110 FAS Treatment Group Assignment in Study 110

Treatment Groups	Description
L200/I-L/I	Subjects randomized/enrolled to L200/I in the previous studies (Study 109 or Study 011B) and enrolled and dosed in Study 110 ^a
P-L/I	Subjects randomized to placebo in Study 109 and enrolled and dosed in Study 110 ^a

I: ivacaftor; L: lumacaftor; P: placebo.

^a Subjects who turn 12 years of age in the previous studies or Day 1 of this rollover study will begin receiving L400/I on Day 1. Subjects who turn 12 years of age after the Day 1 Visit of this rollover study will begin receiving L400/I at their next scheduled visit.

109 Full Analysis Set (109 FAS): The 109 FAS will include all subjects who are randomized and exposed to any amount of study drug in Study 109.

109 Rollover Set (109 ROS): The 109 Rollover Set will include subjects who rolled over from Study 109 (enrolled in Study 110) and were exposed to any amount of study drug in Study 110.

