8.2 Safety Set

Safety Set includes all subjects who are exposed to any amount of study drug in the previous studies. The treatment group will be as treated in the previous studies. The Safety Set treatment group assignment is shown in Table 8-3. For subjects who received study drug from both of the placebo and active treatment groups in Study 109, the treatment group allocation for as-treated analysis will be the L200/I-L/I group.

Table 8-3 Safety Set Treatment Group Assignment in Study 110

Treatment Groups	Description
L200/I-L/I	Subjects dosed with any L200/I in the previous studies (Study 109 or Study 011B)
P-L/I	Subjects dosed with placebo only in Study 109

I: ivacaftor; L: lumacaftor; P: placebo.

^a: Subjects who turn 12 years of age in the previous studies or Day 1 of this rollover study will begin receiving L400/I on Day 1. Subjects who turn 12 years of age after the Day 1 Visit of this rollover study will begin receiving L400/I at their next scheduled visit.

110 Safety Set: The 110 Safety Set will include all subjects dosed in previous studies who are exposed to any amount of study drug in Study 110. The 110 Safety Set treatment group assignment is shown in Table 8-4. For subjects who received study drug from both of the placebo and active treatment groups in Study 109, the treatment group allocation for as-treated analysis will be the L200/I-L/I group.

Table 8-4 110 Safety Treatment Group Assignment in Study 110

Treatment Groups	Description
L200/I-L/I	Subjects dosed with any L200/I in the previous studies (Study 109 or Study 011B) and dosed in Study 110 ^a
P-L/I	Subjects dosed with placebo only in Study 109 and enrolled and dosed in Study 110 ^a

I: ivacaftor; L: lumacaftor; P: placebo.

^a Subjects who turn 12 years of age in the previous studies or Day 1 of this rollover study will begin receiving L400/I on Day 1. Subjects who turn 12 years of age after the Day 1 Visit of this rollover study will begin receiving L400/I at their next scheduled visit.

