10.4.1 Adverse Events

Observational Cohort

For the Observational Cohort, a listing will be presented for all SAEs.

Treatment Cohort Period 1

For Treatment Cohort Period 1, TEAEs will be summarized following the presentation format in Section 10.1.2.1, Table 10-3.

- 1) Previous Study Period based on Safety Set by treatment groups (L200/I and Placebo);
- 2) Current Study Period based on 110 Safety Set by treatment groups (L200/I-L/I and P-L/I) and Overall;
- 3) Cumulative Study Period based on Safety Set with L200/I-L/I, and Current Study Period based on 110 Safety Set with P-L/I, pooled together. The pooled treatment group is presented as L/I Overall.

In TEAE summaries, number and percentage of subjects, as well as exposure-adjusted number of events, will be provided.

For analysis purposes, AEs will be classified as pretreatment AEs, TEAEs, or post-treatment AEs.

- **Pretreatment AE:** any AE that started in the pre-treatment period. The pre-treatment AE will be the same for Previous Study Period and Cumulative Study Period.
- **TEAE:** any AE that increased in severity or that was newly developed in the treatment-emergent period.
- **Post-treatment AE:** any AE that increased in severity or that was newly developed in the post-treatment period.

For AEs with missing or partial start dates, if there is no clear evidence that the AEs started before or after study treatment, then the AEs will be classified as TEAEs. Details regarding handling rules of missing dates are included in Appendix J.

An overview table of the TEAE profile for Treatment Cohort Period 1 will be provided, including total number of TEAEs, with number and percent of subjects and exposure-adjusted number of events in 100PY for the following categories:

- All TEAEs
- Grade 3/4 TEAEs
- TEAEs by relationship
- TEAEs by maximum severity
- TEAEs leading to treatment interruption
- TEAEs leading to treatment discontinuation

- Serious TEAEs
- Related serious TEAEs
- TEAE leading to death

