10.4.8 Spirometry

Treatment Cohort Period 1

Analysis of Predose Spirometry at Each Postdose Visit

Spirometry data will be summarized descriptively as safety-supporting data at each visit during the Cumulative Study Period by treatment group (L200/I-L/I and P-L/I) based on the Safety Set. The following summary (number and percentage of subjects) will be provided:

- Absolute change from previous study baseline in predose ppFEV₁ ≤ -5 percentage points
- Absolute change from previous study baseline in predose ppFEV₁ ≤ -10 percentage points
- Relative change from previous study baseline in predose ppFEV₁ ≤ -5 %
- Relative change from previous study baseline in predose ppFEV₁ ≤ -10 %
- Absolute change from previous study baseline in predose FEV₁ ≤ -0.05L
- Absolute change from previous study baseline in predose FEV₁ ≤ -0.10L
- Relative change from previous study baseline in predose FEV₁ ≤ -5%
- Relative change from previous study baseline in predose FEV₁ ≤ -10%

Subjects with ≥5 percentage points decrease in absolute change from previous study baseline in ppFEV₁ or ≥0.05 L decrease in absolute change from previous study baseline in FEV₁ at any visit during the Cumulative Study Period will be listed based on the Safety Set. The listing will include raw values and absolute/relative changes from previous study baseline in ppFEV₁ and FEV₁ at all visits during the Cumulative Study Period.

Analysis of Serial Spirometry

Based on the 110 Safety Set for the Current Study Period, raw values and absolute change from predose assessment in postdose ppFEV₁ and FEV₁ will be summarized by visit and by time point. The number and percentage of subjects with ≥5, ≥10, ≥15, and ≥20 percentage points decrease in the absolute change from predose to postdose in ppFEV₁ will also be summarized by visit and time point.

The summary tables will include two treatment groups (L200/I-L/I and P-L/I). For treatment L200/I-L/I, separate summaries will also be provided by previous studies (Study 109 and 011B). For both of the summaries, the mean values along with the 95% CIs based on Normal approximation will be plotted against visits and time points.

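### The default safety event tables pool open-label Study 011B into the previous-study L200/I column beside a Study 109-only Placebo column, so the adjacent columns are not a randomised contrast

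*SAP*

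**What the plan says.** SAP 10.1.2.1 gives the default format for categorical safety data in Tables 10-3 and 10-4. The first block is the "Previous Study Period (Studies 109/011B) based on the Safety Set with two treatment groups (L200/I, Placebo"). SAP 10.4.1 repeats it for adverse events: "Previous Study Period based on Safety Set by treatment groups (L200/I and Placebo"). Exposure (10.2.4) and compliance (10.2.5) use the same pair.

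Membership is fixed in SAP 8.2. The population is broad: "Safety Set includes all subjects who are exposed to any amount of study drug in the previous studies". In Table 8-3 the active group is "Subjects dosed with any L200/I in the previous studies (Study 109 or Study 011B"), and the placebo group is "Subjects dosed with placebo only in Study 109".

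The parent studies have different designs. Protocol 8.2.1 states that "Study 109 is designed to compare active treatment (LUM 200 mg q12h/IVA 250 mg q12h) with a matched placebo treatment for 24 weeks", and SAP Table 8-1 confirms that allocation was random: "P-L/I Subjects randomized to placebo in Study 109". Protocol 8.2.2 describes Study 011, including Part B, as open-label, and neither document defines a placebo group for it.

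Elsewhere the SAP takes account of parent study. The MMRM and the rate-of-change models adjust for it (10.3.2.2.1, 10.3.2.2.2). The exacerbation analyses are restricted to Study 109 subjects. For serial spirometry in the L200/I-L/I group, "separate summaries will also be provided by previous studies (Study 109 and 011B").

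**The concern.** A Placebo column beside an active column invites a reader to subtract one from the other. In Study 109 alone that difference would be supported by randomisation. In the planned tables it is not, because a sizeable part of the L200/I column comes from a different study with no placebo group. Any difference in event frequency between the two studies, from whatever cause, would look like a drug effect or would offset one.

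Safety is the primary objective, and these columns carry the adverse-event, special-interest-event and threshold summaries. The event tables have neither the adjustment nor the restriction by parent study that the efficacy analyses have.

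**Working it through.** **The plan's own figure.** The only precision figures are in SAP Table 7-1 (Protocol Table 12-1). The Wald interval p ± 1.96 × √(p(1 − p)/256) reproduces all four rows. At p = 0.2, for example, it gives 0.2 ± 0.049 = (0.151, 0.249). These figures do not bear on the point; they only confirm the planned total of 256.

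**Inputs.** SAP 7.2 gives about 200 subjects from Study 109 and about 56 from Study 011B. These are planned rollover-eligible numbers, not Safety Set counts. The Study 109 allocation ratio is not in the documents; 1:1 is assumed, with 2:1 and 1:2 (active:placebo) as the range. All incidences below are illustrative.

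**Share of Study 011B in the L200/I column**, w = 56/(n + 56), where n is the size of the Study 109 active arm:

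| Allocation | n | Column size | w |
|---|---|---|---|
| 1:1 | 100 | 156 | 35.9% |
| 2:1 | 133 | 189 | 29.6% |
| 1:2 | 67 | 123 | 45.7% |

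**Shift in the column.** Pooled incidence is (n × p109 + 56 × p011B)/(n + 56), so the column moves by w × (p011B − p109).

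- A 10-point gap moves it 0.359 × 10 = 3.6 points (3.0 at 2:1, 4.6 at 1:2).
- A 20-point gap moves it 7.2 points (5.9 to 9.1).
- Masking: suppose Study 109 has 30% on active and 20% on placebo, and Study 011B has 10%. The pooled column shows (100 × 0.30 + 56 × 0.10)/156 = 22.8%. A true +10 points then appears as +2.8 (4.1 at 2:1, 0.9 at 1:2).

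**Against sampling error.** At 20% incidence and 1:1, the standard error of pooled L200/I minus Placebo is √(0.16/156 + 0.16/100) = 5.1 points. A 10-point gap between studies thus gives a shift below one standard error, and a 20-point gap a shift above one.

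**A documented asymmetry.** Under SAP 9.1.1, the previous-study treatment-emergent period of a subject dosed in Study 110 closes at the earliest of 28 days after the last parent-study dose, the end of the period, or the first Study 110 dose. With same-day rollover, which the SAP expects for most subjects, it closes at about Week 24 for Study 109 and about Week 26 for Study 011B. The 2-week washout is therefore inside the Study 011B event window. Exposure under 10.2.4 stops at the last dose, at about Week 24 in both studies. At constant hazard and 1:1:

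- Events per 100PY in the pooled column are multiplied by (100 × 24 + 56 × 26)/(156 × 24) = 3856/3744 = 1.030.
- A 24-week incidence of 20.0% becomes 1 − 0.8^(26/24) = 21.5% in Study 011B, and (100 × 0.200 + 56 × 0.2147)/156 = 20.5% in the pooled column.

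Neither change involves any drug effect.

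**Cost of separating the studies.** At 20% incidence the 95% half-width of the difference is 1.96 × √(0.16/100 + 0.16/100) = 11.1 points for 100 vs 100, against 10.0 points for 156 vs 100.

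**The case against.** The case for leaving the tables alone has force. SAP 10.4 makes safety descriptive, with no testing, and Tables 10-3 and 10-4 have no difference column. The objective is long-term safety, not drug against placebo. The block is openly headed 109/011B, and Table 8-3 says where the placebo subjects come from. Pooling by drug received also fits the L/I Overall column.

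A reader might infer more than the documents support:

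- *That the randomised safety comparison is destroyed.* It is absent from this display, not from the data. SAP 10.3.2.2.2, writing about exacerbations, refers to a two-arm Study 109 final CSR.
- *That every categorical safety table is affected, or that this is the only placebo reference.* The format applies unless otherwise specified. Predose spirometry categories (10.4.8) and continuous safety tables (10.1.2.2) instead show L200/I-L/I and P-L/I over the Cumulative Study Period, which includes placebo-phase visits, although their active group also combines the two studies. Placebo-period exacerbations are analysed in Study 109 subjects only.
- *That a blinded study is mixed with an unblinded one, in different populations.* The documents call Study 109 randomised with matched placebo, but never blinded. Both studies are described as enrolling children aged 6 through 11 homozygous for F508del. The documented differences are design, washout and the Week 26 follow-up.
- *That 10.4.8 already makes this split.* Its split is of the L200/I-L/I group in the Current Study Period, not of a parent-study column beside placebo.

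These limits reduce the weight of the point but do not remove it. Descriptive tables are read by comparing columns, and pooling for total exposure does not require the pooled column to be the one set beside Placebo.

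**Conclusion.** The point holds as a matter of presentation. In the default categorical safety tables, previous-study L200/I against Placebo is not a randomised contrast, and no Study 109-only safety event table is planned in this SAP. No test or formal conclusion is invalidated; what is at stake is misreading.

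The size depends on the allocation ratio, on planned rather than actual counts, and on between-study gaps for which the documents give no figure. At 1:1, Study 011B is about 36% of the column and each 10-point gap moves it about 3.6 points, against a standard error of about 5.1. The washout effect of about 3% on events per 100PY is small, but it follows from the SAP's own window and exposure rules, given same-day rollover and constant hazard.

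**What to change.** In Tables 10-3 and 10-4, divide the 109/011B block into three columns: 109 L200/I, 109 Placebo and 011B L200/I. Keep pooled L200/I only as an added total. Make the matching change in SAP 10.1.2.1, 10.2.4, 10.2.5 and 10.4.1, and in the sections that use the 10.1.2 format: 10.4.3 to 10.4.6 by cross-reference, and the 10.4.2 threshold tables by default. Membership can stay as treated under SAP 8.2, so the Study 109 pair would follow randomisation except for any child who received both placebo and active drug.

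The change affects SAP wording and table shells and needs no new data. It costs wider tables and a small Study 011B column with imprecise percentages. The loss of precision in the Study 109 comparison is slight, as the half-widths above show.
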